2.2 Potential Risks and Benefits

Table 3 SNA002 benefit and risk assessment

	Evidence and uncertainty	Conclusion and reason
Analysis of current status	
 - China has the highest numbers of new cancer cases and cancer deaths in the world. - The top 10 most prevalent malignant solid tumors are lung cancer, gastric cancer, colorectal cancer, liver cancer, breast cancer, oesophageal cancer, thyroid cancer, cervical cancer, brain tumor, and pancreatic cancer, which altogether account for 76.6% of total cancers. - Cancer incidence is rising at a rate of 3.9% annually. - PD-1 is an important immune checkpoint. Studies have found that many tumors can express PD-L1, which can specifically bind to PD-1 on tumor-specific CD8+ T cell surface to suppress their immune response and thereby achieve immune evasion. - Blocking PD-1/PD-L1 signaling pathway can treat tumors. - There are currently several marketed PD-1/PD-L1 drugs that are used for the treatment of NSCLC, metastatic melanoma, and bladder cancer. - The efficacy of mAbs varies greatly (16–100%) among individual cancer patients. 	
It has significant implications in the screening of immunotherapy responders- Patients who respond to immunotherapy can be effectively identified using the nuclear medicine and molecular tracing.
 
- Molecular imaging with such purpose has already become the hot topic of study.

	
 - They have up to 90% efficacy in PD-1/PD-L1-positive patients. 	
Current treatment methods	
 - IHC is still the only method for the detection of PD-1 and PD-L1 expression. - This method has several limitations: (1) IHC is an invasive method that requires the acquisition of tissue specimens and the preparation of tissue sections for pathological examination. biopsy cannot be performed on some tumors. (2) IHC results only reflect the PD-1 and PD-L1 expression in the pathological sections and cannot show the PD-1 and PD-L1 expression in distant metastases and throughout the body. (3) IHC detection is complicated and cannot be used for the monitoring of PD-1 and PD-L1 expression during the course of treatment and prognosis. (4) The detected levels of PD-1/PD-L1 expression are easily influenced by previous treatments of the patients. 	
 - IHC is currently the only detection method. - Immunohistochemistry has drawbacks such as invasive examination, inability to dynamically express overall PD-L1 levels, and high heterogeneity.
Expected benefits	
 - Radionuclide labeling of immunotherapeutic drug molecules and real-time and in vivo detection using molecular imaging methods can provide new strategies for patient screening, efficacy detection, treatment regimen optimization, and prognosis evaluation. - Netspot and Detectnet for neuroendocrine tumor imaging have been approved by the FDA for marketing. - SNA002 has a good ability to bind to PD-L1 receptor and can be used as an in vivo radiodiagnostic agent after coupling with the multifunctional chelator p-SCN-Bn-NOTA and labeling with ⁶⁸Ga to achieve in vivo localization of PD-L1-positive expressing lesions in solid tumor patients and is suitable for PET scanning. - [⁶⁸Ga]Ga-NOTA-SNA002 combined with PET detection of PD-L1-positive tumors can effectively predict the efficacy and outcome of patients, and help to develop individualized treatment plans. 	
 - Nuclear medicine molecular tracer technology can provide a new strategy for screening patients who respond to PD-1/PD-L1 immunotherapy, optimizing tumor anti-PD-1/anti-PD-L1 treatment regimens, and evaluating prognosis. - Current evidence demonstrates that SNA002 is favorable for the screening of PD-1/PD-L1-positive subjects and is therefore urgently needed in clinical setting
Risks	
 - Radiation exposure is the main risk of this product - The radioactive element used in this product is ⁶⁸Ga and its dose is about 5 mCi. - Although SNA002 is a nano-molecule with extremely low immunogenicity, clinical trial observations are still needed to ascertain its potential risks. 	
 - The risk of radiation exposure is small and within the acceptable range.

Conclusion: The main risk (primarily radiation exposure) of the SNA002-based PET imaging diagnostic method is low. This method can noninvasively detect and evaluate PD-1 and PD-L1 expression in tumors, identify the temporospatial heterogeneity in tumors, simplify the complexity and reduce the time and cost of IHC detection, effectively improve the diagnosis and detection rates of tumor, provide new strategies for positive patient screening, treatment regimen optimization, and prognosis evaluation, and bring new insights to the clinical diagnosis and treatment of cancer.

3 Objectives and Purpose

Primary objectives

- To evaluate the safety and tolerability of single doses of SNA002 administered intravenously in patients with solid tumors
- To assess the biodistribution of SNA002 in patients with solid tumors

Secondary objectives

- To assess the radiation dosimetry of SNA002 in patients with solid tumors
- To assess the radiation dose of SNA002 in the blood of patients with solid tumors
- To explore the PET imaging characteristics of SNA002 in patients with solid tumor
- To identify the optimal dose
- To identify optimal image timing window

Exploratory objectives

- To explore the correlation between SNA002 uptake in tumor lesions and PD-L1 expression as determined by immunohistochemistry.
- To explore the positive and negative predictive efficacy of [⁶⁸Ga] Ga-NOTA-SNA002.

4 Study Design and Endpoints

4.1 Description of the Study Design

This is an open-label, single center, dose escalation study to evaluate the safety, PK, biodistribution, dosimetry, and tumor targeting potential of ⁶⁸Ga-NOTA-SNA002 in patients with solid tumors.

4.2 Study endpoints

Primary Endpoints

- Incidence of treatment-emergent adverse events (TEAEs) and serious adverse events (SAEs)
- Dosimetry and biodistribution

Secondary Endpoints

- Radiation dosimetry of SNA002
- Radiation exposure: detecting radioactivity in the blood
- Recommended diagnostic dose of SNA002
- Optimal imaging window
- SUV_{max} (Standardized uptake value), SUV_{mean}, tumor to background ratio, and tumor to blood ratio.
- PK parameters of SNA002: Including but not limited to maximum serum concentration (C_{max}), time to reach maximum serum concentration (T_{max}), and area under the serum concentration versus time curve from time zero to time (AUC_{0-τ}), and terminal half-life (T_{1/2}).
- Immunogenicity: incidence of anti-drug antibodies

5 Study Enrollment and Withdrawal

5.1 Inclusion criteria

Patients must meet all the following criteria to be eligible for participation in this study:

- 1) Male or female patients, 18-75 years of age, inclusive.
- 2) Willing and able to provide signed and dated informed consent prior to any study-related procedures and willing and able to comply with all study procedures.

- 3) Histologically or cytologically confirmed solid tumors including but not limited to non-small cell lung cancer, breast cancer, esophageal cancer, head and neck carcinoma, ovary cancer and melanoma (with or without metastasis); Patients are allowed to enter the study at first diagnosis, at relapse or under treatment.
- 4) Obtain pathological results within one year.
- 5) Patients with the imaging results showing at least 1 tumor lesion that can be sampled by biopsy (enhanced CT, enhanced MRI or ^{18}F -FDG PET/CT results are acceptable).
- 6) ECOG PS 0-2 (See [Appendix 1](#) for details).
- 7) Adequate hepatic function as evidenced by meeting all the following requirements:
 - a) Total bilirubin (TBIL) $\leq 2.5 \times \text{ULN}$.
 - b) Aspartate aminotransferase (AST) and alanine aminotransferase (ALT) $\leq 3 \times \text{ULN}$.
- 8) Serum creatinine $< 1.5 \times \text{ULN}$ and blood urea nitrogen (BUN) $\leq 1.5 \times \text{ULN}$.
- 9) Adequate hematological function defined as:
 - a) White blood cell $3.0-10.0 \times 10^9/\text{L}$ in prior to study entry
 - b) Absolute neutrophil count $1.5-7.0 \times 10^9/\text{L}$ without growth factor support in prior to study entry
 - c) Hemoglobin $\geq 90\text{g/L}$ without transfusion in prior to study entry
 - d) Platelet count $75-300 \times 10^9/\text{L}$ without transfusion in prior to study entry
- 10) Coagulation tests, defined by the following:
 - a) Activated partial thromboplastin time (PTT) $\leq 1.5 \times \text{ULN}$
 - b) International normalized ratio (INR) $\leq 1.5 \times \text{ULN}$.
- 11) Blood pressure value $<$ grade 1 hypertension (including patients with a history of hypertension whose systolic blood pressure is $< 140 \text{ mmHg}$ and diastolic blood pressure is $< 90 \text{ mmHg}$ after exercise or drug treatment).
- 12) Baseline heart rate 60-100/minute (inclusive)

5.2 Exclusion criteria

Patients who meet any of the following criteria cannot be enrolled:

- 1) Patients are unable to conduct visits or undergo relevant examinations, surgeries, or biopsies in accordance with the provisions of this clinical trial protocol.
- 2) Extremely poor nutritional status, $\text{BMI} < 18.5$, unable to tolerate the test subjects.
- 3) Patients with known or suspected evidence of active autoimmune diseases (diagnosed as vitiligo, diabetes, residual hypothyroidism due to autoimmune diseases requiring hormone replacement therapy only, autoimmune disease such as psoriasis that does not require systemic treatment), Or diseases that are not expected to recur in the absence of external triggers are allowed to be included in the study).

- 4) Patients receiving high-dose hormones, such as hydrocortisone exceeding 20mg or prednisone 5mg in the morning, and hydrocortisone exceeding 10mg or prednisone 2.5mg at night;
- 5) Patients with symptomatic brain metastases.
- 6) Patients with known to be severely allergic to [⁶⁸Ga]Ga-NOTA-SNA002, similar drugs or excipients.
- 7) With severe illnesses or other malignant tumors (excluding those who have recovered one year ago or do not require additional treatment).
- 8) Active severe infections (excluding chronic bronchitis clinical remission).
- 9) Serum virology check: One of hepatitis B virus surface antigen, hepatitis C virus antibody, and syphilis-specific antibody results is positive or the human immunodeficiency virus antibody cannot be confirmed negative.
- 10) Total protein <50g/L or albumin<30g/L at screening
- 11) Unable to provide pathological results of biopsy samples;
- 12) History of other severe diseases: ① cardiovascular disease, such as acute myocardial infarction/myocardial infarction within 1 year, acute myocarditis, acute pancarditis, acute heart failure, chronic heart failure NYHA heart function class \geq II (see [Appendix 2](#) for details), CCS class II or higher stable angina pectoris (see [Appendix 3](#) for details), unstable angina pectoris, rheumatic heart disease, malignant arrhythmia [ventricular tachycardia/ventricular fibrillation, frequent ventricular premature beats (more than 5 beats in one minute), II/III degree atrioventricular block, rapid atrial fibrillation/atrial flutter (ventricular rate > 110 beats/min)]. ② brain disease, such as cerebral hemorrhage/cerebral infarction (excluding lacunar infarction), history of epilepsy, pituitary/hypothalamic lesions. ③ lung disease (except lung cancer patients), such as asthma, acute obstructive pulmonary infection, acute bronchitis or acute tracheobronchitis. ④ liver disease (except liver cancer patients), such as cirrhosis (child-pugh score more than 7 points) (see [Appendix 4](#) for details), etc.
- 13) Participants in any other clinical trial within 3 months before screening (excluding participants who only participated in the screening of this clinical trial and have not used the investigational drug).
- 14) Drug/alcohol abuse, severe mental disorders.
- 15) Patients have received high-dose radiation therapy or annual radiation dose >50 mSv within 1 year (inquire about their previous radiation therapy and radiation examination within 1 year, and record them in the screening medical record).
- 16) Patients with claustrophobia, emotional lability, acute persistent spasms, or inability to keep their arms supine for 15 to 30 minutes.

- 17) Female subjects who are pregnant or lactating, or female subjects who have had unprotected sex within 2 weeks before screening, or with positive blood pregnancy test; male subjects (or their partners) or female subjects who have fertility plan or sperm or egg donors throughout the trial and within 6 months after the end of the study, and are unwilling to take contraceptive measures during the trial and within 6 months after the end of the study.
- 18) Women of childbearing age do not use sufficient non hormonal contraceptive methods.
- 19) Any condition that the investigator or primary physician believes may not be appropriate for participating the study.

5.3 Withdrawal or Termination

5.3.1 Reasons for Withdrawal or Termination

The investigator can decide to require an enrolled subject to withdraw from the study if one of the following situations is observed and makes the subject unsuitable for continued participation:

- The investigator determines that the volunteer must stop participation due to medical and ethical concerns.
- The investigator determines that the subject is no longer suitable for continued participation due to SAEs.
- The investigator determines that withdrawal is most beneficial for the subject.
- The subject has poor compliance and is unable to abide with the protocol specifications.

5.3.2 Handling of Participant Withdrawals or Termination

The subject has the right to withdraw during any stage of the study as specified by the ICF.

Regardless of the reason for withdrawal, the reason for subject withdrawal should be recorded and all observations should be completed and reported as detailed as possible.

5.4 Premature Termination or Suspension of Study

According to CTCAE (5.0), the clinical trial should be terminated if over one half of the subjects have grade 2 or greater investigational drug-related AEs or if one case of investigational drug-related SAE is observed.

- Major errors are identified in the clinical trial protocol during the trial, which render drug evaluation difficult.
- Termination requested by the sponsor under the premise that the interests and safety of the subjects are fully guaranteed.
- Trial termination ordered by the NMPA or Ethics Committee due to some tests.
- Inability to recruit patients.
- Lack of imaging even after dose adjustment.

Regardless of whether the trial is terminated by the sponsor or the investigator,

- The investigator should return all investigational drugs, eCRF and relevant trial materials to

the sponsor.

- The sponsor or the investigator should provide a written statement on the reason for early trial termination and inform all principal investigators related to this trial, the Ethics Committee, and NMPA as soon as possible. In addition, all subjects should be informed of the termination of the trial.

5.5 Criteria for Discontinuation from Study

- Patient withdraws consent; no further data will be collected or analyzed in such patients after the date of withdrawal.
- Patient completes all protocol-required procedures and follow-ups through the end of study
- Investigator's discretion.
- Non-compliance with the protocol.
- End of the study.
- Death.

6 Study Agent

6.1 Study Agent and Control Description

6.1.1 Acquisition

Protein part of study agent used in the test is provided by Suzhou SmartNuclide Biopharmaceutical Co., Ltd. The complete drug is configurated with $^{68}\text{Ge}/^{68}\text{Ga}$ generator at GMP environment in nuclear department or shipped to the site after it was configured at the drug dispensing center generator and received by personnel authorized by the principal investigators.

There is no control product in the test.

6.1.2 Formulation, Appearance, Packaging, and Labeling

Investigational drug: Nota ^{68}Ga -labeled recombinant anti-PD-L1 single domain antibody injection (^{68}Ga -NOTA-SNA002). The main active ingredient of this injection is a nanobody protein with a molecular weight of about 14 kDa. This antibody can bind well to PD-L1 without affecting the process of PD-1/PD-L1-mediated immunosuppression and can effectively locate tumor tissues.

^{68}Ga is a positron-emitting radionuclide generated by the $^{68}\text{Ge}/^{68}\text{Ga}$ generator with a half-life of 68 min and an electron decay rate of 89%. ^{68}Ga is suitable for the labeling of small molecule drugs that can rapidly distribute and reach the targets in vivo, and the labeling method is easy, mild, and rapid.

The radiation dose for all dose groups at the time of administration should be ranged from 37 to 200MBq.

Upon completion of the test drug configuration, the lead canister used shall be equipped with an external label for the test drug. Aside from the name of the drug, the external label of drug should also include the words "for clinical trials only", as well as the usage and dosage, active ingredient

manufacturing number, radiolabeling, calibration time, expiry date(at least displayed to minutes), storage conditions, and precautions, etc. Since SNA002 is a radiopharmaceutical, the external label should also have a radiopharmaceutical label. The study drug will be supplied in an open-label manner. An example of the external label design is shown below:

Clinical Study NO: SN-SNA002-2023-001

[⁶⁸Ga]Ga-NOTA-SNA002 (for clinical trials only)

Subject enrollment number: _____

[TIndication]: [⁶⁸Ga] Ga-NOTA-SNA002, as a radiodiagnostic drug, is suitable for detecting PD-L1 positive lesions in solid tumor patients in combination with PET imaging.

[Route of administration]: Slow intravenous administration, time of injection should be no less than 1 min

[Dosage]: _____ mg

[Volume]: _____ ml

[Activity]: _____ MBq

[Calibrated time]: _____ MM _____ DD _____ YYYY _____ HH _____ MM

[Active ingredient manufacturing batch number]: _____

[Expiry date]: _____ MM _____ DD _____ YYYY _____ HH _____ MM

[Storage]: Store at room temp erature in a lead container

[Precautions]: Radioactive substances

Caution: New Drug - Limited by Federal (or United States) law to investigational use.

Figure 1 An example of drug label

[⁶⁸Ga] Ga-NOTA-SNA002 is a radiopharmaceutical, and the drug dish should be equipped with an inner label, which can be slightly introduced, but the drug name and dose should still be labeled. The handwriting of the inner label shall be clearly visible, and it shall be ensured that the injector can still identify it through the drug dish shield. If it cannot be guaranteed, the inner label shall be pasted on the outer side of the drug dish shield.

[⁶⁸Ga]Ga-NOTA-SNA002 (for clinical trials only)

[Route of administration]: Slow intravenous administration, time of injection should be no less than 1 min

[Dosage]: _____ mg

[Volume]: _____ ml

[Activity]: _____ MBq

[Calibrated time]: _____ MM _____ DD _____ YYYY _____ HH _____ MM, Within 4 hours from the expiration date to the administration time

[Active ingredient manufacturing batch number]: _____

Figure 2 An example of drug inner label

6.1.3 Product Storage and Stability

The study site should establish a stringent drug management system (designated personnel, designated cabinet, and locked storage) for the management and distribution of the investigational drug, and establish a registration system. The study site should ensure that the storage temperature of the investigational drug is in accordance with specifications and record the storage temperature. If the storage conditions are found to be out of the specified range, the use of the investigational

drug should be immediately ceased and the investigational drug should be independently stored in a dedicated drug disposal lead container. The investigator and the sponsor will discuss and decide whether the investigational drug is still suitable for use based on the actual situation.

The investigational drug should be stored independently in a sealed lead container. The surface radiation of the lead container should be accordance with relevant specifications. Disposed or excess investigational drugs should be placed in a dedicated drug disposal lead container for at least 10 half-lives and then disposed according to conventional medical waste disposal procedures. The management and use of ⁶⁸Ga-NOTA-SNA002 are conducted in accordance with the “SOP for Radiopharmaceutical Management” of the study site.

6.1.4 Preparation

Before use, add 3.2 mL of 0.25 M sodium acetate solution and 0.1 mL of 2 mg/mL cold SNA002 protein sequentially and mix well in a sterile vial. Add a total of 5 mL 0.1 M sterile ⁶⁸Ga washing solution to the vial. Subsequently change the pH of the reaction system to 4.0–4.5. Heat the solution in a metal bath at 37 °C for 20 min to generate the SNA002 injection. The detailed preparation procedures are shown in the “Standard Operating Procedure for the Synthesis of SNA002 Injection”.

The complete drug is configurated with ⁶⁸Ge/⁶⁸Ga generator at GMP environment in nuclear department or shipped to the site after it was configured at the drug dispensing center generator and received by personnel authorized by the principal investigators. Details of the standard synthesis procedures are shown in the “Standard Operating Procedures for the Synthesis of ⁶⁸Ga-NOTA-SNA002 Injection”.

The investigational drug should be used in 4 hours.

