Study Design	
Overall Study Design
 
This is an open-label, dose escalation study to evaluate the safety, PK, biodistribution, dosimetry, and tumor targeting potential of SNA002 in patients with solid tumors.
 
This study will consist of Screening Period, Baseline Period, Study Period and Safety Follow-up Period. A signed and dated informed consent form will be obtained before any study-related procedures are performed. Collect CT/MRI/PET/CT results from subjects within one month before screening to obtain baseline tumor assessment. Eligible patients will be enrolled at least two days before the administration of study drug. The radiation dose for all dose groups at the time of administration should be ranged from 37 to 200MBq. Four dose levels of NOTA-SNA002 are planned: 0.1mg, 0.3mg, 0.5mg and 0.9mg. The final drug product administered to the patient is [⁶⁸Ga]Ga-NOTA-SNA002. Three to seven patients will be sequentially enrolled into each dose cohort. Patients will be administered a single dose of SNA002 over 1 minute as an intravenous bolus. Patients will be observed for 6±1h and 24±6h post infusion for infusion-related and other adverse reactions. In the first cohort of patients, whole body imaging will be acquired using PET/CT at 15±5 minutes, 60±10 minutes and 120±20 minutes post-injection. Before each imaging, the patients need to empty bladder as much as possible. Total-body PET-CT scans can be performed on 1-2 subjects in a certain dose group or each dose group, covering at least one of the aforementioned time points. In the subsequent cohorts,

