6.1.5 Dosing and Administration

Dose of investigational drug: This trial will include 3–4 dose groups, namely the 0.1 mg, 0.3 mg, 0.5 mg and 0.9 mg dose groups. The dose of protein should be adjusted according to the imaging results of the previous dose group during the trial. The radiation dose for all dose groups at the time of administration should be ranged from 37 to 200MBq.

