6.1.6 Route of Administration

Administration method: aspirate [⁶⁸Ga]Ga-NOTA-SNA002 using a syringe and slowly administer by intravenous injection. The injection time should be no less than 1 min. An indwelling needle should be inserted into the subject before intravenous push. followed by extubation after bolus injection of 10 to 20 ml of normal saline, and clinical routine radiation protection treatment was performed on the indwelling needle and syringe. Subjects were instructed to drink no less than 500 mL of water well for hydration multiple times prior to dosing. Subjects should drink and excrete multiple times after dosing to reduce radiation exposure.

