6.1.7 Starting Dose and Dose Escalation Schedule

6.1.7.1 Starting Dose

SNA002 does not bind to mouse, rat and dog PD-L1. Therefore, cynomolgus monkey was chosen in biodistribution studies and repeat-dose general toxicity studies. ^{68}Ga -NOTA-SNA002 can specifically bind to PD-L1 proteins of primates, and the radioactivity uptake is low in other organs except for the excretion organs (kidneys and bladder). The estimated absorbed dose (effective dose) converted from cynomolgus monkeys to adult male or female is 0.022-0.023mSv/MBq, which shows good radiation safety. The recommended dose of ^{68}Ga -NOTA-SNA002 for clinical trials is 185 MBq (5mCi), which generates an effective dose of about 4.1 mSv indicating safe use of ^{68}Ga -NOTA-SNA002 for clinical diagnostics. A NOAEL approach based on the pivotal monkey 2-week study toxicity findings was used to determine the maximum recommended starting dose (MRSD) for the first in human study. In the 2-week monkey study, the potential infusion reaction is the only toxicity observed after 3 repeated iv doses. the dose of 1.5 mg/kg (mean $\text{AUC}_{0-t} = 20700 \text{ ng}\cdot\text{h}/\text{mL}$; mean $\text{C}_{\text{max}} = 32000 \text{ ng}/\text{mL}$) and 0.5mg/kg (mean $\text{AUC}_{0-t} = 5060 \text{ ng}\cdot\text{h}/\text{mL}$; mean $\text{C}_{\text{max}} = 10500 \text{ ng}/\text{mL}$) was considered the NOAEL for males and females, respectively. Since the molecular weight of ^{68}Ga -NOTA-SNA002 is less than 100KD, The HED is 0.48 mg/kg (male) and 0.16 mg/kg (female) based on body surface. The MRSD is considered to be 0.048 mg/kg (male) and 0.016 mg/kg (female) (1/10 of NOAEL). The highest dose that nonclinical can cover is considered to be 0.24 mg/kg (male) and 0.08 mg/kg (female) (1/2 of NOAEL). The proposed human dose ranges are from 0.00167 mg/kg (0.1mg flat dose) starting dose to the highest ascending dose 0.01503mg/kg (0.9mg flat dose). The starting dose is 28.74- and 9.58-fold lower than the MRSD for males and females, respectively. The highest ascending 0.01503 mg/kg is covered by nonclinical data ($\frac{1}{2}$ of the NOAEL). Therefore, the proposed clinical mass dose range of 0.00167mg/kg to 0.01503mg/kg is not expected to pose a significant risk to patient safety.

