6.1.10 Tracking of Dose

SNA002 will only be intravenously injected once in the trial.

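### Section 6.1.4 prints one unqualified recipe containing 0.2 mg of protein, which matches none of the planned dose levels and is below three of the four; unless the unseen synthesis SOPs explain it, the text needs reconciling

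*Combined protocol and SAP*

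**What the plan says.** The Study Design part of the protocol summary states: "Four dose levels of NOTA-SNA002 are planned: 0.1mg, 0.3mg, 0.5mg and 0.9mg". Section 6.1.5 lists the same levels, "namely the 0.1 mg, 0.3 mg, 0.5 mg and 0.9 mg dose groups", and adds: "The dose of protein should be adjusted according to the imaging results of the previous dose group during the trial". Section 6.1.7.1 treats the two ends of the range as flat doses per patient, describing it as running from 0.00167 mg/kg (0.1 mg) as the "starting dose to the highest ascending dose 0.01503mg/kg (0.9mg flat dose"). Section 6.1.10 allows one administration: "SNA002 will only be intravenously injected once in the trial".

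Section 6.1.4 then gives the preparation as an instruction: 3.2 mL of sodium acetate solution, "0.1 mL of 2 mg/mL cold SNA002 protein sequentially and mix well in a sterile vial", then 5 mL of the gallium-68 solution, pH adjustment and heating. It names no dose group. It refers to two SOPs for preparation and synthesis detail, and neither is among the documents. The label templates in section 6.1.2 leave blank fields for mg, mL and MBq.

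**The concern.** The dose groups are defined by protein mass; the radioactivity range is the same for all of them (6.1.5). Section 6.1.7.2 identifies the optimal dose by comparing image quality between mass levels, with 0.3 mg against 0.1 mg as its worked example, and the recommended diagnostic dose is a secondary endpoint (4.2). A reader should be able to follow how the mass for each group is made up. The one recipe in the protocol contains a mass that is not a planned level and is smaller than most of them.

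The protocol labels illustrations elsewhere: the source-organ list in the summary and the two label figures in 6.1.2 are called examples. The recipe carries no such marker, so as printed it reads as applying to every group.

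**Working it through.** The protocol states no protein mass per vial, so there is no printed figure to reproduce. The check multiplies volume by concentration and compares the result with each planned level.

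Inputs:
- Protein volume 0.1 mL and concentration 2 mg/mL: section 6.1.4.
- Planned levels 0.1, 0.3, 0.5 and 0.9 mg: summary (Study Design) and 6.1.5; the 0.1 and 0.9 mg ends are called flat doses in 6.1.7.1.
- One injection per patient: 6.1.10.

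Step 1. Protein in one preparation = volume x concentration = 0.1 mL x 2 mg/mL = **0.2 mg**.

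Step 2. Compare with each level:

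| Planned level (mg) | 0.2 mg as share of level | Level divided by 0.2 mg |
|---|---|---|
| 0.1 | 0.2/0.1 = 200% | 0.5 |
| 0.3 | 0.2/0.3 = 67% | 1.5 |
| 0.5 | 0.2/0.5 = 40% | 2.5 |
| 0.9 | 0.2/0.9 = 22% | 4.5 |

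The last column only expresses the size of the mismatch; it is not a proposed way of preparing the drug.

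Step 3. Could the text close the gap for the upper three levels? Repeat injections are ruled out by 6.1.10. That leaves more protein in the vial or several preparations pooled. Section 6.1.5 says that the protein dose is adjusted, which implies that something changes. No available section says what changes in the vial or mentions pooling.

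Step 4. Could the recipe serve the lowest level? Yes. By mass, 0.1/0.2 = half of one preparation. Section 6.1.6 has the drug drawn up "using a syringe and slowly administer by intravenous injection", which allows a partial draw. Section 6.1.3 foresees leftover drug ("Disposed or excess investigational drugs should be placed in a dedicated drug disposal lead container"), although that is a disposal provision and only weak support for a planned partial draw.

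Step 5. What can be checked against the label? The mg field can be compared directly with the four planned levels. The mL field cannot: the protocol prints no injected volume per group, and the volume used for pH adjustment is not stated, so the final volume does not follow from the text.

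**The case against.** The strongest reply is that a clinical protocol need not carry radiolabelling quantities for every group. Section 6.1.4 expressly sends the reader to two SOPs, and 6.1.5 shows that the protein amount is not fixed. On that reading the recipe is an outline whose quantities the SOPs vary, and what is missing is drafting detail. Much of this stands. The SOPs may well scale the protein by group, and their absence from the documents is no evidence that they do not. What does not fall away is the text itself. If the SOPs scale the amount, they differ from the unqualified quantity printed beside the reference to them, and 6.1.4 should say so.

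A second reply is that the labels protect the dose-group comparison. This also largely stands. The outer label carries the subject enrollment number with mg, mL and MBq, and the inner label must still show the dose. The recorded mass can be checked against the planned level, and only the volume lacks a printed reference.

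A third reply is that comparing 0.2 mg with a patient's dose assumes one preparation per patient. That is correct: 6.1.10 limits injections, not preparations. The percentages therefore describe one preparation made as printed, not a shortfall in what a patient would receive.

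A reader might go further and infer that patients in the 0.3, 0.5 and 0.9 mg groups would be underdosed, or that the trial has no method for making those doses. The documents support neither inference, for the reasons just given.

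**Conclusion.** The point holds as an internal inconsistency. The only printed recipe contains 0.2 mg of protein, equals none of the four planned levels, and in one preparation supplies 67%, 40% and 22% of the 0.3, 0.5 and 0.9 mg levels. The 0.1 mg level is compatible with it by partial draw. The quantity is printed without qualification and bears on the variable that defines the dose groups, so this is more than missing detail.

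The practical consequence is limited and may be nil if the SOPs already set the amount by group. The product of 0.2 mg is exact. The comparison assumes that the recipe's protein and the planned levels are the same mass measure; the summary writes NOTA-SNA002 and 6.1.4 writes SNA002 protein, but 6.1.5 speaks of the protein dose when it lists the levels. Which quantities are right cannot be judged from the documents.

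**What to change.** The sponsor should reconcile section 6.1.4 with 6.1.5, the summary and the two synthesis SOPs, in one of two ways: either the printed protein quantity and volume agree with each planned level, or 6.1.4 states that its quantities are an example and that the SOPs set the amount by group. Which quantities are correct is for the sponsor to state.

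The formal SAP, which section 10.1 says is still to be completed, should add one line: the protein mass recorded on each patient's label is used to confirm the dose group in the analysis.

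The cost is a wording amendment and a check against existing SOPs. No patients or procedures are added, because the labels already have mg and mL fields.
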